3.3 Study Oversight for Safety Evaluation

A subject may elect to discontinue study drug at any time for safety, medical, or personal reasons. Patients who choose to discontinue study drug prior to disease progression will be followed in the post study treatment follow up period and continue to undergo regularly scheduled disease assessment until documentation of disease progression or start of an alternative anticancer treatment. All subjects who discontinue study drug will be followed for overall survival and all post progression cancer treatments administered will be recorded. Subjects may at any time withdraw consent for further study participation. No further data will be collected on subjects once consent has been withdrawn. The investigator will promptly explain to the subject involved that the study drug will be discontinued for that subject and provide appropriate medical treatment and other necessary measures for the subject. A subject who has ceased to return for visits will be followed up by mail, phone, or other means as much as possible to gather information such as the reason for failure to return and the status of treatment compliance, presence or absence of adverse events, and clinical courses of signs and symptoms, and the information will be recorded in the CRF.

Subjects who discontinue early from the study or treatment will be discontinued for 1 of these primary reasons: adverse event(s), lost to follow-up, subject choice, progressive disease, or administrative/other. In addition to the primary reason, the subject may have indicated 1 or more of these reasons as secondary reasons for discontinuation. Study disposition information will be collected on the appropriate CRF. A subject removed from the study for any reason may not be replaced.

Safety will be assessed by monitoring and recording all AEs including all CTCAE grades (for both increasing and decreasing severity) and serious adverse events (SAEs); regular monitoring of hematology, clinical chemistry, and urine values; physical examinations; and regular measurement of vital signs, and electrocardiograms (ECGs) as detailed in the schedule of visits and procedures.

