- Additional new unequivocal lesions at the confirmatory PD time point compared with the first time point at which new lesions were identified.

In the absence of clinically significant deterioration, the Investigator should continue study treatment until progression is confirmed.

Clinical Study Protocol
Drug Substance DURVALUMAB/TREMELIMUMAB
Study Number ESR 15-11561-61-DUNE
EudraCT N°: 2016-002858-20
Edition Number: 5.0 dated on June 09th, 2021

If progression is not confirmed, then the patient should continue on study treatment and on treatment assessments.

Modification of RECIST as described may discourage the early discontinuation of durvalumab + tremelimumab and provide a more complete evaluation of its anti-tumor activity than would be seen with conventional response criteria. Nonetheless, the efficacy analysis will be conducted by programmatically deriving each efficacy endpoint based on RECIST 1.1 criteria.

Of note, clinically significant deterioration is considered to be a rapid tumor progression that necessitates treatment with anti-cancer therapy other than durvalumab + tremelimumab or with symptomatic progression that requires urgent medical intervention (e.g., central nervous system metastasis, respiratory failure due to tumor compression, spinal cord compression).

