Data cut-off for the primary study analysis will happen following after the last patient included in the study has performed the first tumor evaluation (week 12 after first dose of study drug). The following tumor evaluations will take place every 12 weeks until documentation of disease progression or start of another anticancer therapy.

Analysis of primary efficacy variable

The analysis of clinical benefit rate and overall survival rate will be performed independently for each study cohort when the last patient included in the corresponding cohort of the study will arrived to 9 months after inclusion in the study or have progressed. The primary objective of the study will be based on the investigator assessment.

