	Day (±3)	Months (±1 week)						12 Months and every 6 Months (±2 weeks)
		30	2	3	4	6	8	
Physical examination ^a	x	x	x	x	x	x	x	
Vital signs (temperature, respiratory rate, blood, pressure, pulse)	x	x	x	x	x	x	x	
Weight	x	x	x	x	x	x	x	
Urine hCG or serum βhCG	x							
AE/SAE assessment	x	x	x					
Concomitant medications	x	x	x					
Palliative radiotherapy	As clinically indicated							
ECOG performance status	x	x	x		x (and month 9)			x
Subsequent anti/cancer therapy	x	x	x	x	x	x	x	
Survival status: phone contact with subjects who refuse to return for evaluations and agree to be		x	x	x	x	x	x	x (every 2 months)

Clinical Study Protocol
 Drug Substance DURVALUMAB/TREMELIMUMAB
 Study Number ESR 15-11561-61-DUNE
 EudraCT N°: 2016-002858-20
 Edition Number: 5.0 dated on June 09th, 2021

contacted							
Hematology	x	Every 8-12 weeks, according to investigator's criteria					x
Serum chemistry	x	Every 8-12 weeks, according to investigator's criteria					
Thyroid function tests (TSH, and fT3 and fT4) ^b	x	Every 8-12 weeks, according to investigator's criteria					
SPD-L1 concentration (to assess target engagement)		x					
Tumour assessment (CT or MRI)	
For subjects who achieve disease control following 12 months of treatment, tumour assessments should be performed every 12 weeks relative to the date of first infusion thereafter until confirmed PD by RECIST 1.1 by investigational site review. Please refer to SCHEDULE OF STUDY ASSESSMENTS for timings of confirmatory scans.
 
For subjects who discontinue study drug due to toxicity (or symptomatic deterioration), tumour assessments should be performed relative to the date of first infusion as follows: every 12 weeks until confirmed PD by RECIST 1.1 by investigational site review. Please refer to SCHEDULE OF STUDY ASSESSMENTS for timings of confirmatory scans.
 
Upon confirmed PD, scans should be conducted according to local standard clinical practice until a new treatment is started (these scans are optional).
						
^a Full physical exam ^b Free T3 and free T4 will only be measured if TSH is abnormal. They should also be measured if there is clinical suspicion of an adverse event related to the endocrine system. ^c For patient questionnaires different approaches based on indication and study design.							

Appendix 3 Schedule of study procedures: follow-up for subjects who have discontinued durvalumab or tremelimumab treatment due to confirmed progression of disease at the investigator discretion

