3.7.3 Planned Method of Analysis

Summary tables (descriptive statistics and frequency tables) will be provided for all baseline variables, efficacy variables, and safety variables, as appropriate. Continuous variables will be summarized with descriptive statistics (mean, standard deviation, range, and median). Ninety-five (95) percent confidence intervals (95% CI) may also be presented, as appropriate. Frequency counts and percentage of subjects within each category will be provided for categorical data.

The primary efficacy analysis will be performed using the binomial test procedure. Missing data will be treated using statistical multiple random imputation.

Concordance between investigator assessment and independent central radiology review will be analyzed using Cohen's Kappa. Although no significant differences are expected, a sensitivity analysis for the primary efficacy analysis will be performed using as response variable independent central radiology assessment.

Secondary endpoints will be summarized with descriptive statistics. Continuous variables will be summarized with n, mean, standard deviation, and range, frequency counts and percentage of subjects within each category will be provided for categorical data. Multivariate regression models will be used to study relations between explanatory variables and primary endpoint. Survival analysis will be performed to analyze PFS, Kaplan-Meier curves will be presented and possible comparisons will be tested using the log-rank test or the Cox proportional hazard model for multivariate analysis, hazard ratios (HR) and their 95% confidence interval (CI95%) will be provided. Patients with lost of follow-up or treatment discontinuation will be included in the final analysis of primary endpoint if they have at least one tumor evaluation and considered as censored data for survival endpoints.

R software version 3.2.1 will be used for all analysis.

Safety Analyses

Safety analyses will be based on the Safety Analysis Set. All safety analyses will be summarized separately by cohort. Adverse events and serious adverse events, laboratory test results, physical examination findings and vital signs, and their changes from baseline will be summarized using descriptive statistics. Abnormal values will be flagged.

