3.7.5 Missing Data

Assuming that the pattern of missingness in the primary endpoint variable (clinical benefit rate at 9 months) are missing at random (1), missing data will be treated using statistical multiple random imputation (2,3,4). Once data are collected, according to the missing data pattern observed, it should be considered if pre-specified methods are appropriate. A full reporting of all reasons for patient discontinuation should be given where possible, in order to identify the most important reasons that caused it. As suggested by the EMA (2), the seed of the pseudorandom number generator that will be used to randomly generate imputations for the missing values is pre-specified ("55881234") to avoid bias being introduced by *post hoc* selection of the seed and therefore the random numbers to be imputed.

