2.1 PRIMARY EFFICACY ANALYSES

The analysis of clinical benefit rate and overall survival rate will be performed independently for each study cohort when the last patient included in the corresponding cohort of the study will arrived to 9 months after inclusion in the study or have progressed. According to the protocol, the primary objective of the study will be based on the investigator assessment. 9-months clinical benefit rate (CBR) by Response Evaluation Criteria In Solid Tumors (RECIST version 1.1), which is defined as the percentage of patients achieving complete response (CR), partial response (PR), or stable disease (SD) at month 9 after durvalumab plus tremelimumab was started.

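### Cohorts 1–3: the month-9 clinical benefit analysis has no failure category for death or new anticancer therapy without documented progression, so such patients could be imputed as benefit or dropped

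*Protocol*

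**What the plan says.** **Endpoint.** For cohorts 1–3 the primary endpoint is "defined as the percentage of patients achieving complete response (CR), partial response (PR), or stable disease (SD) at month 9" (SAP 2.1; Protocol 2.1 agrees), counted from the start of the combination. Neither document says how death or a new anticancer therapy before month 9 is scored.

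**Tables.** The CBR shells in SAP 2.1.1 (Tables 92 and 95) and 2.1.2 (Tables 96 and 99) have two outcome rows: Yes for CR, PR or SD, and No for PD. There is no row for death, new therapy or not evaluable.

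**Missing data.** SAP 3.7.5 assumes that missing month-9 CBR is missing at random, and "missing data will be treated using statistical multiple random imputation". SAP 3.7.3 and Protocol 11.2 repeat the method. None of them makes an exception for patients who died or switched.

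**Who is analysed.** The Full Analysis Set is all allocated subjects (SAP 3.7.1). Yet SAP 3.7.3 and Protocol 11.2 keep patients lost to follow-up or off treatment in the primary analysis only if they have at least one tumour evaluation.

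**When scans stop.** Protocol 3.3 says that patients who choose to stop study drug before progression "continue to undergo regularly scheduled disease assessment until documentation of disease progression or start of an alternative anticancer treatment". Protocol 11.1 and SAP 3.7.2 set scans "every 12 weeks until documentation of disease progression or start of another anticancer therapy". Appendix 2 of the protocol instead continues them "every 12 weeks until confirmed PD by RECIST 1.1 by investigational site review". The protocol's schedule of assessments and section 8.1.3 likewise run to progression or confirmed progression, with no stop at a new therapy.

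**The concern.** A patient who dies before a scan shows progression has no month-9 response. Nor, under Protocol 3.3, 11.1 and SAP 3.7.2, does one who switches therapy before progression is documented. These exits carry information: a patient who died by month 9 cannot be in response or stable then, and a switch often reflects a treatment that is not working.

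The plan gives such a patient no failure category. The written routes are imputation from patients who were assessed, which assigns a positive probability of benefit, or exclusion if there was no tumour evaluation. Both raise CBR, in single-arm cohorts of 31 where a few patients can decide a comparison with a fixed reference rate.

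**Working it through.** **Inputs from the documents.** Cohort size 31, reference rate 30%, expected increase 20 points, superiority margin 10 points, one-sided alpha 5% (Protocol 11.3, SAP 3.6); binomial test (SAP 3.7.3). The plan has no figure of its own for deaths or switches without progression, so there is nothing to reproduce.

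**Assumption.** Let q be the share of a cohort that dies or switches before month 9 without documented progression. It is shown at 5%, 10% and 20%. The planned 10% loss to follow-up is a different quantity and is not an estimate of q.

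**Step 1: direction and size.** Let p be the share of all patients with observed benefit at month 9. Scored as failures, the exits leave CBR at p. SAP 3.7.5 names no imputation model, so I take the simplest one: each exit is imputed at the rate among assessed patients, p/(1 − q). Then

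expected CBR = p + q × p/(1 − q) = p/(1 − q).

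Dropping the exits gives the same expression, because the denominator shrinks to 1 − q.

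| q | p = 0.30 | p = 0.40 |
|---|---|---|
| 5% | 0.30/0.95 = 31.6% | 0.40/0.95 = 42.1% |
| 10% | 0.30/0.90 = 33.3% | 0.40/0.90 = 44.4% |
| 20% | 0.30/0.80 = 37.5% | 0.40/0.80 = 50.0% |

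**Step 2: in patients.** With 10 observed benefits among 31, scoring exits as failures gives 10/31 = 32.3%. With m exits imputed or dropped, the expected rate is 10/(31 − m): 10/29 = 34.5% for m = 2, 10/26 = 38.5% for m = 5, and 10/23 = 43.5% for m = 8.

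**Step 3: effect on the test against 30%.** Exact binomial, n = 31: P(X ≥ 14) = 0.053 and P(X ≥ 15) = 0.024, so at least 15 benefits are needed. Simulation used 20,000 trials with a true CBR of 30%, 20 beta-binomial imputations and the pooled count rounded and held to at least 15. The false-positive rate was about 4%, 7% and 17% at q = 5%, 10% and 20%, against 2.4% when exits are failures. A Rubin-pooled Wald test gave 6.5%, 9.3% and 18.0%, against 5.2% at q = 0.

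**Step 4: can a conclusion flip?** Take 13 benefits among 26 assessed patients and 5 exits (chosen counts). Scored as failures this is 13/31 = 41.9%, short of 15. Imputed at 50%, the expected count is 13 + 5 × 0.5 = 15.5, above 15. If the 10-point margin applies and the null is 40%, at least 18 of 31 are needed (tail probability 0.032; 17 gives 0.068), and neither 13 nor 15.5 passes. The inflation in Step 1 remains; this particular reversal does not.

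**The case against.** **Imputation of deaths is inferred.** No passage says that a patient who died or switched is imputed. A strict reading of the endpoint over all allocated subjects makes a known death a failure, and Protocol 3.3 follows survival after study drug stops. A table row label is not a scoring rule. This stands, so the claim is that such patients *could* be imputed. The strict reading still needs writing down, because the only stated rule for an absent month-9 response is imputation.

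**Scans do not always stop at a switch.** A reader might infer from Protocol 3.3 that they do. Appendix 2, section 8.1.3 and the schedule of assessments say otherwise. In addition, 8.1.3 implies an end-of-treatment scan unless one was done in the previous 28 days, and other cancer therapy is barred during study treatment (Protocol 7.2.2). This narrows the gap for patients who switch, but not for those who die. What stands is an inconsistency.

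**Section 9 does not describe failures without progression.** It says "clinically significant deterioration is considered to be a rapid tumor progression that necessitates treatment with anti-cancer therapy other than durvalumab + tremelimumab", and one might take this as proof of such exits. Its role there is to waive the confirmatory scan once a scan has shown progression, so it is not evidence for this point.

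**A switch is not a failure by definition.** The endpoint is timed from the start of treatment and does not require the patient to remain on it. Scoring a switch as No is a choice of estimand. This stands.

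**The method may be revisited.** SAP 3.7.5 asks whether the pre-specified methods suit the missing-data pattern once data are collected, and for full reporting of discontinuation reasons. In an open-label trial, a decision made after seeing the data is no substitute for a rule set beforehand.

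**Conclusion.** The concern holds in limited form. For cohorts 1–3 the plan gives no failure category for death or new anticancer therapy before month 9 without documented progression. Its written rules would let such patients be imputed as benefit, or dropped if never scanned after baseline, which conflicts with the all-allocated Full Analysis Set. Both routes bias CBR upward by a factor of 1/(1 − q): from a true 30% to about 32–37.5% for q of 5–20%. That size rests on an assumed q and on imputation at the rate among assessed patients. A model using earlier scans could change it, but imputing a known death still contradicts the endpoint.

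A reader might go further and conclude that the rule reverses the primary result. The documents do not support that: no exit rate is given, the counts in Step 4 are chosen, and that reversal disappears if the stated margin is part of the test. Cohort 4 is outside this point, because its primary endpoint is 9-month survival.

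**What to change.** In Protocol 11.2 and SAP 2.1.1 and 3.7.5:

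- Score death from any cause before the month-9 assessment as No in the Full Analysis Set, including patients with no post-baseline scan. Align the requirement for one tumour evaluation in SAP 3.7.3 and Protocol 11.2 with this.
- Score the start of another anticancer therapy before month 9, without a month-9 assessment, as No in the primary analysis, and state it as an explicit estimand choice.
- Restrict multiple imputation to patients who are alive, have not switched and have no month-9 scan.
- Relabel the failure row of Tables 92, 95, 96 and 99 as No (PD, death, other anticancer therapy).

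Separately, the passages on when tumour assessment ends must be reconciled: Protocol 3.3 and 11.1 and SAP 3.7.2 against the protocol's schedule of assessments, section 8.1.3 and Appendix 2.

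The scoring change costs wording and table shells only. Survival and subsequent therapies are already collected (protocol schedule of assessments, note n; Appendix 2). The downside is that the CBR estimate can only become less favourable.

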4. PATIENT SELECTION, ENROLLMENT, ALLOCATION, RESTRICTIONS, DISCONTINUATION AND WITHDRAWAL

Approximately 126 patients will be enrolled and allocated in a balanced manner into either the four cohorts of patients at approximately 20 sites in Spain. Each patient must meet all of the inclusion criteria (Section 4.1) and none of the exclusion criteria (Section 4.2) for this study. Under no

circumstances, will there be exceptions to this rule.

4.1 Inclusion criteria

For inclusion in the study, patients should fulfill the following criteria:

1. Written informed consent obtained from the subject prior to performing any protocol-related procedures.
2. Age > 18 years at time of study entry.
3. Subjects must have histologically confirmed diagnosis of one of the following advanced/metastatic neuroendocrine tumor types:
 - a) **Cohort 1:** Well-moderately differentiated neuroendocrine tumors of the lung (mitotic count ≤ 10 mitoses $\times 10$ HPF), also known as typical and atypical lung carcinoids, that have progressed to prior somatostatin analog therapy and/or one prior targeted therapy or chemotherapy (only one prior systemic therapy, with the exception of patients that have been treated with somatostatin analogues and other systemic treatment, when two prior treatments are allowed).
 - b) **Cohort 2:** Well-moderately differentiated neuroendocrine tumors G1/G2 (WHO grade 1 and 2) gastrointestinal neuroendocrine tumors after progression to somatostatin analogs and one targeted therapy (prior targeted therapy could be everolimus or a multikinase inhibitor). Prior therapies with interferon alpha-2b or radionucleotide therapy are allowed.
 - c) **Cohort 3:** Well-moderately differentiated neuroendocrine tumors G1/G2 (WHO grade 1 and 2) from pancreatic origin after progression to standard therapies (chemotherapy, somatostatin analogs and target therapy); patients must be treated with at least two prior systemic treatment lines and a maximum of four previous treatment lines.
 - d) **Cohort 4:** Neuroendocrine neoplasms (WHO grade 3) of gastroenteropancreatic origin or unknown primary site (excluding lung primary tumors), patients will be treated in second line only, after progression to first-line chemotherapy with a platinum based regimen. Patients will be treated in second line.”
4. For patients included in cohorts 1, 2 and 3: WHO Classification G1/G2 (mitotic count ≤ 10 mitoses $\times 10$ HPF) lung typical and atypical carcinoids for cohort 1, G1/G2 (Ki67 $\leq 20\%$ or mitotic count ≤ 20 mitoses $\times 10$ HPF) gastrointestinal for cohort 2 (including stomach, small intestine and colorectal origins), G1/G2 (Ki67 $\leq 20\%$ or mitotic count ≤ 20 mitoses $\times 10$ HPF) pancreatic for cohort 3.
5. For patients included in cohort 4: WHO classification G3 (Ki67 $\geq 20\%$ or mitotic count > 20 mitoses $\times 10$ HPF) gastroenteropancreatic neuroendocrine carcinomas (NEC) or liver metastases of G3 NEC of unknown primary site.
6. Subjects must have evidence of measurable disease meeting the following criteria:
 - a) In case of more than one target lesion, it should be identified at least 1 lesion of ≥ 1.0 cm in the longest diameter for a non lymph node, or ≥ 1.5 cm in the short-axis diameter for a lymph node, which is serially measurable according to RECIST 1.1 using computerized tomography/magnetic resonance imaging (CT/MRI). If there is only one target lesion and it is a non-lymph node, it should have a longest diameter of ≥ 1.5 cm.

Clinical Study Protocol
 Drug Substance DURVALUMAB/TREMELIMUMAB
 Study Number ESR 15-11561-61-DUNE
 EudraCT Nº: 2016-002858-20
 Edition Number: 5.0 dated on June 09th, 2021

- b) Lesions that have had external beam radiotherapy (EBRT) or loco-regional therapies such as radiofrequency (RF) ablation or liver embolization must show evidence of progressive disease based on RECIST 1.1 to be deemed a target lesion.
- c) Subjects must show evidence of disease progression by radiologic image techniques within 12 months (an additional month will be allowed to accommodate actual dates of performance of scans, i.e., within \leq 13 months) prior to signing informed consent, according to RECIST 1.1.

7. Eastern Cooperative Oncology Group (ECOG) performance status of 0 or 1.

8. Life expectancy of at least 12 weeks.

9. Adequate normal organ and marrow function as defined below:

- Haemoglobin \geq 9.0 g/dL.
- Absolute neutrophil count (ANC) \geq 1.5 \times 10⁹/L (\geq 1500 per mm³).
- Platelet count \geq 100 \times 10⁹/L (\geq 100,000 per mm³).

10. Serum bilirubin \leq 1.5 \times institutional upper limit of normal (ULN). This will not apply to subjects with confirmed Gilbert's syndrome (persistent or recurrent hyperbilirubinemia that is predominantly unconjugated in the absence of hemolysis or hepatic pathology), who will be allowed only in consultation with their physician.

11. AST (SGOT)/ALT (SGPT) \leq 2.5 \times institutional upper limit of normal unless liver metastases are present, in which case it must be \leq 5x ULN.

12. Serum creatinine CL>40 mL/min by the Cockcroft-Gault formula (Cockcroft and Gault 1976) or by 24-hour urine collection for determination of creatinine clearance:

Males:

$$\text{Creatinine CL (mL/min)} = \frac{\text{Weight (kg)} \times (140 - \text{Age})}{72 \times \text{serum creatinine (mg/dL)}}$$

Females:

$$\text{Creatinine CL (mL/min)} = \frac{\text{Weight (kg)} \times (140 - \text{Age})}{72 \times \text{serum creatinine (mg/dL)}} \times 0.85$$

13. Female subjects must either be of non-reproductive potential (ie, post-menopausal by history: \geq 60 years old and no menses for \geq 1 year without an alternative medical cause; OR history of hysterectomy, OR history of bilateral tubal ligation, OR history of bilateral oophorectomy) or must have a negative serum pregnancy test upon study entry.

14. Subject is willing and able to comply with the protocol for the duration of the study including undergoing treatment and scheduled visits and examinations including follow up.

